#### 5.1.2 AE date imputation

According to Novartis-Germany guidelines missing values in dates will be imputed by a simple way:

Missind day → replacement by 15

Missing month → replacement by 7

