## 4 Study design

This is a 12-month, multi-center, open-label, randomized, controlled study to evaluate efficacy and safety and evolution of renal function of everolimus (EVR) in co-exposure with tacrolimus (TAC) in *de novo* liver transplant recipients.

Patients will be consented and screened for eligibility prior to liver transplantation (LTx). The study treatment will start with a run-in period that ends on the day of randomization (RND), scheduled at 7-21 post- LTx. Patients after consent who have undergone successful LTx (with optional induction therapy) will be entered in this run in period (between 3 and 5 days post- LTx) and may be initiated on an optional induction therapy, MMF, TAC at investigators' discretion until at least day 7 or maximally until day 21 post LTx with mandatory CS therapy until at least Month 6 post Tx.

Patients on MMF according to local practice must have the MMF administration discontinued by the time of RND. MMF is discontinued according to local practice.

At day 7-21 post-transplantation the following information at minimum has to be obtained from a patient to be randomized into the study:

- Abbreviated MDRD eGFR > 30 mL/min/1.73m^2. Creatinine results obtained in local laboratory within 5 days prior to RND are acceptable.

All eligible patients (according to in-/exclusion criteria at RND) will be randomized in between 7 and 21 days post LTx to one of the two treatment groups in a 1:1 ratio:

**Arm 1: EVR/TAC group** (Tacrolimus minimization arm)

Everolimus should be initiated at the day of randomization. Therapeutic drug monitoring will be mandatory throughout the duration of the study. Whole blood trough levels should be obtained  $5 \pm 2$  days after either everolimus or tacrolimus doses are changed.

**Everolimus dosing:** Everolimus study drug will be started at the day of randomization at a dose of 1.0 mg b.i.d (2.0 mg daily dose). The everolimus whole blood trough (C-0h) levels should be targeted to be maintained between 3-8 ng/mL. The twice daily dose can be changed in order to maintain the 3-8 ng/mL C-0h levels through the remainder of the study.

**Tacrolimus dosing:** After everolimus whole blood trough levels have been confirmed to be in the target range (3-8 ng/mL), tacrolimus tapering should begin, achieving a target tacrolimus C-0h levels of <5 ng/mL plus corticosteroids by three weeks after randomization and continuing through the remainder of the study.

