### **2.1.1 General definitions**

Study treatment:

- EVR/TAC
- TAC

Date of randomization: Date of Visit 2 (Baseline)

Date of first treatment: max (date of randomization, min (start date of dosage administration\*))

Date of last treatment: Max (max(end date of dosage administration\*), Last known date subject took study treatment~)

\*: documented on Dosage Administration Record form

~: documented on End of Treatment form

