### **2.6.1 Adverse events (AEs)**

Treatment emergent events are defined as all adverse events started at baseline or later.

Treatment emergent adverse events were summarized by presenting, for each treatment group, the number and percentage of patients having any adverse event, having an adverse event in

each body system and having each individual adverse event. Any other information collected (e.g. severity or relatedness to study medication) were listed as appropriate.

Data collected by AE CRFs and by Infection CRFs were coded using MedDRA. The number of AE/patients with AE was summarized by MedDRA system organ class and preferred term. Additionally, AE will be summarized

- by maximum severity,
- for AE with suspected drug relation,
- for serious AE (SAE), and
- for AE leading to permanent discontinuation of study drug.

In addition to being analyzed together with AE data, the incidence of bacterial, viral and fungal infections will be tabulated separately for all infections

- by maximum severity,
- for infections with suspected drug relation,
- for serious infections and
- for infections leading to premature discontinuation of study drug.

Infections were defined as adverse events as adverse events in primary system organ class “Infections and infestations”.

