**Changes in statistical methods in comparison to the protocol:**

The Virus (HCV, CMV) and Hepatocellular Carcinoma (HCC) related secondary objective “• To evaluate rates of progression of HCV related allograft fibrosis are deleted. Reason is, that the in case from HCV the biopsies were not performed adequately.

The incidence of proteinuria of  $0.5 - <1.0$  g/day,  $1.0 - <3.0$  g/day and  $\geq 3.0$  g/day could not be analysed, because in urine analysis protein is measured in g/l and not in g/day. Therefore, proteinuria could be only documented as adverse event. Therefore proteinuria is defined as further adverse event of special interest.

CNV viral infection were defined as further adverse event of special interest.

Treatment emergent events were defined as all adverse started at baseline or later.

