#### 5.1.3 Concomitant medication date imputation

According to Novartis-Germany guidelines missing values in dates will be imputed by a simple way:

Missing day → replacement by 15

Missing month → replacement by 7

In the analysis of Immunosuppressive Medications, the medication tacrolimus and everolimus will be excluded.

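### Partial AE dates are set to day 15 and month 7 without reference to randomisation, so the treatment-emergent flag can be wrong in both directions

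*SAP*

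**What the plan says.** SAP 5.1.2 cites an in-house guideline under which "missing values in dates will be imputed by a simple way". The whole rule is "Missind day → replacement by 15" and "Missing month → replacement by 7"; SAP 5.1.3 applies the same values to concomitant medication. Neither section mentions randomisation, first dose, visit date or the end date of the event.

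SAP 2.6.1 then states: "Treatment emergent events are defined as all adverse events started at baseline or later". SAP section 4 repeats this among the changes from the protocol: "Treatment emergent events were defined as all adverse started at baseline or later". The AE summaries rest on the flag: "Treatment emergent adverse events were summarized by presenting, for each treatment group, the number and percentage of patients having any adverse event". SAP 2.1.1 equates the randomisation date with the date of Visit 2 (Baseline). Under Protocol section 4, patients are "randomized in between 7 and 21 days post LTx", so baseline can fall on any calendar day.

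Protocol 10.5.2 keeps AEs that are not treatment-emergent out of the summary tables but in the listings. SAP 2.1.1 does take a maximum with the randomisation date, but only when deriving the date of first treatment. Neither document gives a similar floor for AE dates.

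**The concern.** The flag compares a start date with baseline, and for a partial date the start is a fixed calendar value unrelated to baseline. Two examples:

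- A patient is randomised on 20 March and has an AE on 25 March, recorded as March only. It is dated 15 March, before baseline, and leaves the treatment-emergent tables.
- A patient is randomised on 1 October and has an AE in November, recorded by year only. It is dated 15 July and also leaves the tables.

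The reverse happens when randomisation falls on or before the 15th, or on or before 15 July: a pre-randomisation event from the same month or year is moved to baseline or later. Such records exist, because Visit 2 collects events since the previous visit (Protocol section 7) and SAEs are reported from consent (Protocol 8.1).

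AE frequency is one of the two main bases of the safety assessment (SAP 2.6). With only the day missing, the outward error is confined to the calendar month of randomisation. That is when everolimus is started and, once its level is confirmed, tacrolimus is tapered (Protocol section 4).

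**Working it through.** The plan states no figure on this point, so there is none to reproduce. The rule was applied literally to a calendar.

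**Inputs from the documents:** imputed day 15 and month 7 (SAP 5.1.2); treatment-emergent means start on or after baseline (SAP 2.6.1); 360 days of follow-up (Protocol Table 4-1).

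**Assumptions, not in the documents:** randomisation uniform over the 365 days of a non-leap year; onset uniform over the window considered. The 30-day window after randomisation and the 21-day window before it are chosen for illustration. All shares apply only to AEs whose start date is partial.

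**Day missing, moved out.** An AE is moved out if randomisation is on day D > 15 and onset is later in the same month, which leaves L − D + 1 onset days in a month of length L.
- Exposed randomisation dates: 7×16 + 4×15 + 13 = 185 of 365 (50.7%).
- Patient-days affected: 7×(16×17/2) + 4×(15×16/2) + 13×14/2 = 952 + 480 + 91 = 1,523. All fall within 30 days of randomisation.
- Onset in the first 30 days: 1,523/(365×30) = 1,523/10,950 = **13.9%**.
- Onset over 360 days: 1,523/(365×360) = 1,523/131,400 = **1.2%**.

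**Day and month missing, moved out.** 15 July is day 196, so 365 − 196 = 169 randomisation dates (46.3%) are exposed. These have 169, 168, …, 1 onset days left in the same year.
- First 30 days: (30×31/2 + 139×30)/10,950 = 4,635/10,950 = **42.3%**.
- 360 days: (169×170/2)/131,400 = 14,365/131,400 = **10.9%**.

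**Moved in, onset in the 21 days before randomisation** (denominator 365×21 = 7,665).
- Day missing: randomisation on day D ≤ 15 moves in D − 1 days: 12×(0 + 1 + … + 14) = 12×105 = 1,260; 1,260/7,665 = **16.4%**.
- Day and month missing: randomisation on or before 15 July moves in up to 21 days: 210 + 175×21 = 3,885; 3,885/7,665 = **50.7%**.

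**After the fix below.** Flooring at randomisation whenever the known part of the date matches leaves 0 post-randomisation AEs dated before baseline, in both cases. The price is paid on the other side. Before any end-date exception, every partial-date AE from the 21 days before randomisation that falls in the matching period becomes treatment-emergent:
- Day missing: 7×420 + 4×399 + 357 = 4,893; 4,893/7,665 = 63.8%. The terms are the sums of min(21, D − 1) over months of 31, 30 and 28 days.
- Year only: 210 + 344×21 = 7,434; 7,434/7,665 = 97.0%.

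**Medication.** SAP 2.3.2 defines prior medication by a start at least one day before randomisation, but concomitant medication by use on at least one day between randomisation and last study treatment. A start imputed too early therefore leaves a drug concomitant as long as its end date falls after randomisation. The error is mainly an added prior label.

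**The case against.** The strongest case against is that the effect is small and not shown to favour either arm.

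- With only the day missing, about 1% of such AEs move out over the year covered by the AE tables. This stands. Restricting the denominator to day-missing AEs in the calendar month of randomisation raises the share to about 26% (1,523/5,738, where 5,738 = 7×496 + 4×465 + 406). That describes a narrow subset and should not be the headline.
- Year-only dates should be rare. AEs are sought at every visit, start and end dates are required items (Protocol 7.6.1), and omissions are queried (Protocol 9.3). This also stands, so the 42% and 11% apply to what is probably a very small group.
- A patient leaves a table row only if no other event keeps them in it, and misplaced AEs should still appear in the listings. This stands.

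A reader might infer that treatment-emergent AEs are undercounted overall, or that the comparison between arms is biased. The documents support neither. Errors run in both directions, the net balance depends on unknown numbers of partial dates on each side of baseline, and the rule is identical in both arms. Nor do the documents show that AEs are densest just after randomisation; the first week after transplant precedes baseline by design.

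None of this removes the conflict itself. The SAP's date rule can contradict its own treatment-emergent definition, and no other text in either document prevents it.

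**Conclusion.** The point holds as a correctable defect in the safety derivations. Applied as written, SAP 5.1.2 gives wrong treatment-emergent flags in both directions for some partial dates. The size is conditional on a date being partial and on uniform randomisation dates and onset. For day-missing AEs, about 14% (first 30 days) or 1% (360 days) move out, and about 16% from the preceding 21 days move in. For year-only dates, about 42% and 11% move out. The absolute effect is unknown because the number of partial dates is not given.

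The primary eGFR analysis and the sample size are untouched. For medications, the consequence is mainly a wrong prior label.

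**What to change.** In SAP 5.1.2, add: if the known part of an AE start date matches the month and year of randomisation (Visit 2), or the year when only the year is known, use the later of the imputed date and the randomisation date, unless a known (not imputed) AE end date is before randomisation. Otherwise keep the current imputation. Anchor on randomisation rather than first dose, because baseline defines treatment-emergence.

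Report by arm the number of AEs with imputed start dates, so that readers can judge how much rests on the rule.

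The cost is a few lines in the SAP and in the date-handling code, plus a rerun of any AE tables already produced. The downside is that some truly pre-baseline AEs will count as treatment-emergent. That is the conservative direction for safety, and the end-date exception limits it.

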#### 5.1.3 Concomitant medication date imputation

According to Novartis-Germany guidelines missing values in dates will be imputed by a simple way:

Missing day → replacement by 15

Missing month → replacement by 7

In the analysis of Immunosuppressive Medications, the medication tacrolimus and everolimus will be excluded.

## 5.2 Analysis of the primary objective

Missing values in eGFR will be imputed with the last valid observed value from that patient (LOCF). That means the eGFR values will be carried forward in case of missing. For that procedure the visits will be ordered by date of visit. If the treatment are discontinued, the visit 9a (End-of-treatment visit) will be performed. This additional visit will also be ordered after the last performed visit under treatment.

According to this procedure, the last present eGFR values until Month 12 is used as primary endpoint for all patients. Please note, that in case of treatment discontinuations, the last value is not under treatment.

## 5.3 AEs coding/grading

Adverse events were analysed by MedDRA, version 20.0.

## 5.4 Laboratory parameters derivations

The values from the local values are documented in different units per parameter. The values were converted to standard units. The statistical analysis will be done by the converted values.

## 5.5 Statistical models

### 5.5.1 Primary analysis

The primary analysis is an analysis of covariance (ANCOVA) with treatment, center, HCV-Class (positive, negative) and lab MELD ( $\leq 30$  vs  $> 30$ ) as factors, and eGFR at Visit 2 (Baseline) as covariate:

```
ods output LSMeans=LSMeans; *** LSMeans+CL for effects ***;
ods output Estimates=Estimates; *Estimates+CL for contrasts;
proc glm data=&data;
  class tgplc ctrln;
  model egfr = baseline tgplc HCV_class lab_MELD_class / ss3;
  lsmeans tgplc / stderr ;
  estimate "mean difference" tgplc 1 -1;
run;
quit;
```

HCV-Classification: If in screening or baseline one HCV serology assessment (HCV or HCV-IgG) in recipient is positive, the patient is classified as positive, otherwise as negative

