## 6.4 Treatment assignment

At Baseline (Visit 2), which has to take place prior to randomization, all patients who meet the inclusion and do not fulfill any of the exclusion criteria will be given the lowest available number on the randomization list of the respective stratum. This number assigns them to one of the treatment arms. The investigator will enter the randomization number on the CRF.

The randomization numbers will be generated using the following procedure to insure that treatment assignment is unbiased and concealed from patients and investigator staff. A

randomization list will be produced under the responsibility of the Novartis Nürnberg GCP Officer using a validated system that automates the random assignment of treatment arms to randomization numbers in the specified ratio. Randomization will be stratified by HCV status (positive/negative) and lab MELD (Model of End Stage Liver Disease) score below/equal or above 30 at transplantation.

Randomization of individual patients will be performed centrally by a CRO. Allocation of a patient to one of the two treatment groups will be performed in the following steps.

1. Information about patient enrolment (Screening Visit):

Study sites will inform the CRO about each patient inclusion via fax

2. Randomization (Baseline Visit):

At day of randomization, the site will provide the information of eligible patient to the CRO by fax.

The CRO will allocate the patient the next free consecutive randomization number allocated to the site. Randomization number and allocated treatment (according to the randomization list) will be provided to the site by fax.

The randomization number will be entered on the CRF of an individual patient.

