### **10.4.2 Statistical hypothesis, model, and method of analysis**

The trial tests the null hypothesis that the treatment difference (investigational minus control) in mean eGFR at Month 12 after baseline is zero versus the alternative hypothesis that the treatment difference is different from zero.

The hypotheses will be tested with an analysis of covariance (ANCOVA) with treatment , center, HCV-Class (positive, negative) and MELD ( $\leq 30$  vs  $> 30$ ) as factors, and eGFR at Visit 1 (Baseline) as covariate. Raw as well as adjusted means (= LS-means, LS: least square means) will be presented for the treatment contrast together with a two-sided *p* value and the appropriate confidence interval, respectively. The significance level will be 5% (two-sided). There are no multiplicity issues to be addressed since only the hypothesis of superior efficacy of the investigational vs. the control regimen will be tested confirmatory.

The Full Analysis Set will be used for the primary analysis. If patients of the FAS are switched from the reference to the investigational group during the study, they will be analyzed in their randomized group. If appropriate, a subgroup analysis will be performed comparing patients of the reference group with and without switch to the investigational group including a further analysis comparing the subgroups to the randomized investigational group. If treatment will be modified in the investigational group, they will be analyzed as randomized.

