### 1.3.1 Subgroup of interest

For the analysis of the primary anaylsis the following fixed factors were included in model:

- HCV-(IgG), measured at screening in viral serology: positive vs. negative
- Lab MELD, measured at screening: <=30 vs >30

Descriptive statisitics for

Descriptive statistics for the primary efficacy variable were presented for the following subgroups:

- age: <60 vs.  $\geq$ 60 years
- gender: male vs. female
- renal function at baseline: 30 – <45, 45 – <60,  $\geq$ 60 mL/min/1.73m^2;
- renal function at baseline: <45 vs  $\geq$ 45 mL/min/1.73m^2,
- renal function at baseline <60 vs.  $\geq$ 60 mL/min/1.73m^2
- HCV status at baseline: positive vs. negative
- lab MELD score at baseline:  $\leq$ 14, 15 – 19, 20 – 24, 25 – 29,  $\geq$ 30

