### **2.3.4 Statistical hypothesis, model, and method of analysis**

The trial tests the null hypothesis that the treatment difference (investigational minus control) in mean eGFR at Month 12 after baseline is zero versus the alternative hypothesis that the treatment difference was different from zero.

The hypotheses was tested with an analysis of covariance (ANCOVA) with treatment , center, HCV-Class (positive, negative) and lab MELD ( $\leq 30$  vs  $> 30$ ) as factors, and eGFR at Visit 2 (Baseline) as covariate. Raw as well as adjusted means (= LS-means, LS: least square means) were presented for the treatment contrast together with a two-sided p value and the appropriate confidence interval, respectively. The significance level was 5% (two-sided). There are no multiplicity issues to be addressed since only the hypothesis of superior efficacy of the investigational vs. the control regimen was tested confirmatorily.

The Full Analysis Set was used for the primary analysis. Patients will be analyzed in their randomized group.

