### 5.5.2 Key secondary analysis

*Multiple imputation (Molenberghs & Kenward 2007; White, Royston & Wood 2010)*

Alternative to LOCF, additionally as sensitivity analyses a multiple imputation (Molenberghs & Kenward 2007; White, Royston & Wood 2010) is planned:

\* Impute values via MCMC to obtain a monotone missing pattern\*;

```

proc mi data=&data out=gfr_mono n impute=20 seed=579415 NOPRINT
  by tgplc;
  mcmc chain=multiple impute=monotone;
  var v:;
run;

** Impute values via predictive mean matching *;
proc mi data=gfr_mono out=gfr_imp n impute=1 seed=579214 NOPRINT;
  by tgplc _imputation_;
  monotone regpmm;
  var v:;
run;

ods output LSMeans=LSMeans; *** LsMeans+CL for effects ***;
ods output Estimates=gfr_imp; *LsMeans+CL for contrasts;
proc glm data=gfr_imp;
  by _imputation_;
  class tgplc ctr1n;
  model egfr_im = baseline tgplc HCV_class lab_MELD_class / ss3;
  lsmeans tgplc / stderr ;
  estimate "mean difference" tgplc 1 -1;
run;
quit;

*lsmeans;
proc sort data=LSMeans;
  by tgplc;
run;

ods listing close;
ods rtf exclude all;
ods output ParameterEstimates=LSMeanMI;
proc mianalyze data=LSMeans;
  by tgplc;
  modeleffects lsmean;
  stderr stderr;
run;
*lsmean difference;
proc sort data=LSMeanDiff;
  by parameter;
run;

ods output ParameterEstimates=LSMeanDiffMI;
proc mianalyze data=LSMeanDiff;
  by parameter;
  modeleffects estimate;
  stderr stderr;
run;

```

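### The printed code for the primary ANCOVA leaves centre out of the MODEL statement, although the protocol and SAP text specify centre as a factor

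*SAP*

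**What the plan says.** Three places in the text specify centre as a factor:

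- Protocol 10.4.2: the hypotheses "will be tested with an analysis of covariance (ANCOVA) with treatment , center, HCV-Class" and MELD as factors, and baseline eGFR as covariate.
- SAP 2.3.4 repeats this: "analysis of covariance (ANCOVA) with treatment , center, HCV-Class (positive, negative) and lab MELD".
- SAP 5.5.1, directly above the program: "The primary analysis is an analysis of covariance (ANCOVA) with treatment, center, HCV-Class (positive, negative) and lab MELD".

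The program in SAP 5.5.1 then declares "class tgplc ctrln" and fits "model egfr = baseline tgplc HCV_class lab_MELD_class / ss3". The multiple-imputation program in SAP 5.5.2 likewise names a centre variable in CLASS and fits "model egfr_im = baseline tgplc HCV_class lab_MELD_class / ss3".

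SAP 1.3.1 introduces a list with "For the analysis of the primary anaylsis the following fixed factors were included in model" and names HCV and lab MELD, but not centre. The list of changed statistical methods in SAP Section 4 does not mention centre.

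**The concern.** In PROC GLM a variable named only in CLASS is not fitted as an effect. The printed program therefore tests treatment in a model with baseline eGFR, HCV class and MELD class. The text describes that model plus centre. These give different estimates, standard errors and p-values, and this is the trial's only confirmatory test.

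The ambiguity spreads. The per-protocol analysis (SAP 2.3.6) and the analyses of the other eGFR formulas (SAP 2.5.2) are defined by reference to the primary model. The multiple-imputation analysis, which the Note to File says was programmed and reported, has the same omission.

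Some between-centre variation is plausible because creatinine is measured in local laboratories (Protocol 7.6.4). Baseline eGFR from the same laboratory will remove part of it.

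A smaller point: the text calls HCV class and MELD class factors, but neither is in CLASS. With two-level numeric coding the treatment contrast is unaffected.

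**Working it through.** **Text against code.**

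| Term | Protocol 10.4.2 | SAP 2.3.4 | SAP 5.5.1 text | SAP 5.5.1 MODEL | SAP 5.5.2 MODEL |
|---|---|---|---|---|---|
| Treatment | yes | yes | yes | yes | yes |
| Baseline eGFR | yes | yes | yes | yes | yes |
| HCV class | yes | yes | yes | yes | yes |
| MELD class | yes | yes | yes | yes | yes |
| Centre | yes | yes | yes | **no** | **no** |

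**Sample size.** Protocol 10.7 uses a two-group t-test with difference 7.0, SD 18, two-sided 5% and 80% power. The noncentral-t power is 0.797 at 104 per group and 0.801 at 105, so 105 is reproduced. The plan's drop-out formula gives 105/(1 − 0.20)² = 164.06, so 165. Neither figure involves covariates, so neither depends on the centre term.

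**Degrees of freedom.** With 330 patients, the code's model has 5 parameters: 330 − 5 = 325 error df. Fifteen centres (Protocol 5) add 14 terms: 325 − 14 = 311. The critical t goes from 1.9673 to 1.9676.

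**Size of the effect.** The documents give no between-centre variance, centre sizes, block size or baseline correlation. The following are assumptions:

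- 330 patients in 15 centres of 4 to 60
- SD 18 and baseline correlation 0.5
- 20% HCV positive and 15% with MELD above 30
- blocks of 4
- centre holding 0, 5 or 10% of residual variance

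The standard error without centre should then be about 18 × √(1 − 0.5²) × √(2/165) = 15.59 × 0.110 = 1.72, and 1.96 × 1.72 ≈ 3.4 is the difference at the edge of significance.

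Protocol 6.4 names HCV and MELD strata, but also says "The CRO will allocate the patient the next free consecutive randomization number allocated to the site". Whether allocation was balanced within site is therefore unclear, and both cases were simulated (30,000 trials per row). The move is the absolute change in the treatment estimate, in mL/min/1.73m², between the two models. Disagreement means that only one model gives p < 0.05.

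| Blocks within | Centre share | SE without / with centre | Mean move (95th percentile) | Type I error without centre | Disagree, true 7.0 | Disagree, true 3.4 |
|---|---|---|---|---|---|---|
| Site | 5% | 1.719 / 1.681 | 0.085 (0.22) | 0.045 | 0.23% | 2.7% |
| Site | 10% | 1.713 / 1.636 | 0.098 (0.25) | 0.041 | 0.33% | 4.1% |
| HCV × MELD only | 0% | 1.718 / 1.756 | 0.29 (0.73) | 0.049 | 0.8% | 6.5% |
| HCV × MELD only | 5% | 1.713 / 1.712 | 0.40 (1.01) | 0.050 | 1.1% | 9.2% |
| HCV × MELD only | 10% | 1.710 / 1.666 | 0.49 (1.24) | 0.051 | 1.2% | 11.6% |

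With site-balanced allocation, omitting centre makes the standard error about 2% (1.719/1.681) to 5% (1.713/1.636) too large, which works against showing a difference. Without site balance, the estimate itself moves.

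A third reading is HCV × MELD strata within each site. At centre shares of 5 to 10% it falls in between: moves of 0.17 to 0.20, and disagreement in about 4 to 6% of trials at 3.4 and under 1% at 7.0.

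**Sensitivity (centre share 5 to 10%).** For baseline correlations of 0.3 and 0.7, the mean move without site balance is 0.32 to 0.55, and the SE excess with site balance is 2.2 to 4.8%. Fifteen equal centres of 22 give an SE excess of 2.2 to 5.0% and a move of 0.41 to 0.51.

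**The case against.** The strongest reply is that text and code conflict, but this does not prove a slip or show which model was run. SAP Section 4 is not a complete log: it also omits the removal of the baseline requirement from the FAS definition (Protocol 10.1, SAP 1.2). No model program in the SAP contains centre, although the MMRM text does not ask for it. The printed code has other defects. For example, the multiple-imputation program sorts a dataset that it never creates. On this view the code is a sketch and the prose, stated three times, governs. SAP 1.3.1 sits under a subgroup heading and also omits treatment, so it is weak evidence of a competing model.

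Much of this is fair. The documents do not show which program was run, and silence in Section 4 does not separate accident from intent. SAP 1.3.1 carries little weight alone.

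The magnitude also needs care. Without site balance, a move of 0.29 and 6.5% disagreement at 3.4 arise even when centre explains nothing, simply from fitting 14 further terms. More than half of the 0.40 to 0.49 move is therefore not a centre effect. The largest disagreement rates also apply at a difference chosen to lie on the significance boundary.

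None of this removes the mismatch. Whatever the cause, the SAP supports two primary models, and the reader cannot tell which one produced the result.

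**Conclusion.** The concern holds. The program printed for the primary analysis does not fit the model that the protocol and SAP text specify, and no change is recorded. The unused centre variable in CLASS suggests a dropped term, but intent cannot be settled from the documents.

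The consequence is modest. Type I error without centre stays at 0.041 to 0.051, the planned sample size stands, and no bias is expected. What is lost is a single pre-specified result: some precision if sites were balanced, or an estimate shifted by roughly 0.4 to 0.5 mL/min/1.73m² if they were not. Significance would seldom change at a true difference of 7.0, but could in a borderline result. These sizes rest on the assumed centre variance, centre sizes, block size and baseline correlation. The mismatch itself rests on no assumption. It should be fixed, but does not by itself undermine the trial.

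**What to change.** - Add the centre variable to the MODEL statements in SAP 5.5.1 and 5.5.2. Confirm its name first: the two programs spell it differently (`ctrln` and `ctr1n`), possibly through text conversion.
- If the analysis has been run, state which model gave the primary p-value and report the model specified in the text.
- If centre was left out on purpose, record that and the reason in SAP Section 4 and correct SAP 2.3.4 and 5.5.1.
- Optional tidying: name centre in SAP 1.3.1, and declare HCV class and MELD class in CLASS to match the text.

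**Cost.** One term in each of two statements, and a re-run if the programs were already used. Centre uses up to 14 of 325 error df. If centre explains nothing and sites were not balanced, the standard error rises by about 2% (1.756/1.718).

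Moving HCV and MELD into CLASS has a side effect, because default LSMEANS weights class levels equally. Each arm's adjusted mean shifts by (0.5 − p) × coefficient for a proportion p positive. With an assumed coefficient of 5, that is 2.0 at p = 0.1 and 1.0 at p = 0.3. The shift is the same in both arms, so the contrast does not change, and the OM option keeps the observed weights.
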